Currently, there is no widely accepted prediction model that reliably allows clinicians to determine the risk of a patient developing AFACS, despite multiple efforts over the past 15 years to develop one (25–31). Published AFACS prediction models are limited by small sample sizes, a failure to include modern variables and a lack of external prospective validation (26,27,29,32–36). Moreover, our team and others have previously developed AFACS risk prediction models that suffer from limited generalizability, oversimplification, and the fact that they often use information from variables that occur after surgery, or even after onset of AFACS (22,35,37). A recent analysis showed the best area under the receiver operator characteristic curve (AUROC) for any of the published prediction models was 0.68 (95% confidence interval [CI]: 0.67–0.69) (38,39), just marginally better than a model which only included age (0.66, 95% CI: 0.65–0.68) (22). The work emphasised the importance of using representative and detailed multicentre data sets to develop prediction models and prospectively validating these on multiple cohorts.

The lack of effective pre and immediate post-operative prediction models for estimating AFACS risk has prevented the implementation of AF prophylaxis protocols (38). Interventions to prevent AFACS lead to decreased hospital length of stay, lower costs of hospital treatment, and decreased risk of post-operative stroke (40). Pharmacological (e.g., Amiodarone, beta blockers, electrolyte supplementation) and non-pharmacological (e.g., atrial pacing, posterior pericardiotomy, botulinum toxin) therapies provide practical methods to significantly reduce AFACS incidence (2). In selected patients, some peri-operative prophylactic therapies reduce the risk of AFACS (41,42), and have been included in guidelines (43–46). However, these interventions are not effective in all patients and some have a high risk of adverse side effects. Therefore, it is crucial to use clinical information to target interventions to those individuals at highest risk of developing AFACS, who will more likely benefit from prophylaxis. Furthermore, monitoring patients after hospital discharge shows significant numbers of early asymptomatic recurrences. These patients are often at high risk of stroke and may benefit from anticoagulation for stroke prevention.

Improved prediction of AFACS could facilitate targeted monitoring that is more likely to identify AFACS recurrence (1).

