11.7 The Level of Statistical Significance

The level of statistical significance will be set at p<0.05.

11.8 Procedure for Accounting for Missing, Unused, and Spurious Data.

To avoid excluding patients when developing and validating our models, we will use multiple imputation to impute missing values, under a missing at random assumption. Identifying the true underlying missing data mechanism from the available is rarely possible. Assumptions need to be made on the plausible mechanism, and approaches needed to be used. Under a missing completely at random mechanism.

Clinical Research Protocol Template version 15.0 CON © Copyright: The University of Oxford and Oxford University Hospitals NHS Foundation Trust 2019 Page 21 of 34

CONFIDENTIAL

(MCAR), the missingness mechanism does not depend on unobserved (unseen) data. Carrying out a complete case analysis will produce unbiased estimates (but with a loss precision if full data are observed). Under the missing at random (MAR) assumption, the missingness after conditioning on the observed data does not depend on the unobserved (unseen) data. Under this approach, we can apply approaches such as multiple imputation, by fitting a joint model to the observed data and impute the missing data, taking account of the uncertainty in the estimated parameters of this joint model. We feel this, MAR, approach makes a less strong and more realistic assumption than the MCAR approach. The MAR imputation model will include all variables considered for the multivariable model building, the outcome and any auxiliary variables that will help explain the missingness. The assumption of a missing not at random (MNAR) approach whilst not implausible is considerably more complex to investigate – there is a dearth of research investigating MNAR in the context of prediction model research. We will nevertheless explore whether the MAR assumption holds by comparing the imputed values (after accounting for the observed values) and the missing values to identify if there are any systematic differences to suggest a MNAR assumption.

Data from the NHS Trusts provide a large "real-world" prospective validation, but is likely to contain more missingness (60).

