#### 3.4. GENERAL ISSUES FOR STATISTICAL ANALYSIS

#### 3.4.1. METHOD FOR HANDLING MISSING DATA

To avoid excluding patients when developing and validating our models, we will use multiple imputation to impute missing values, under a missing at random assumption.

Identifying the true underlying missing data mechanism from the available is rarely possible. Assumptions need to be made on the plausible mechanism, and approaches needed to be used. Under a missing completely at random mechanism. (MCAR), the missingness mechanism does not depend on unobserved (unseen) data. Conducting a complete case analysis will produce unbiased estimates (but with a loss precision if full data are observed). Under the missing at random (MAR) assumption, the missingness after conditioning on the observed data does not depend on the unobserved (unseen) data. Under this approach, we can apply approaches such as multiple imputation, by fitting a joint model to the observed data and impute the missing data, taking account of the uncertainty in the estimated parameters of this joint model.

We feel this, MAR, approach makes a less strong and more realistic assumption than the MCAR approach. The MAR imputation model will include all variables considered for the multivariable model building, the outcome and any auxiliary variables that will help explain the missingness. The assumption of a missing not at random (MNAR) approach whilst not implausible is considerably more complex to investigate – there is a dearth of research investigating MNAR in the context of prediction model research. We will nevertheless explore whether the MAR assumption holds by comparing the imputed values (after accounting for the observed values) and the missing values to identify if there are any systematic differences to suggest a MNAR assumption.

Therefore, to conform to current guidelines[34], multiple imputation for all subjects with at least one missing value (using the 'mice' function in R, for example) will be used.

Data from LHCH and BHC provide a large "real-world" prospective validation but is likely to contain more missingness [35].

Using sensitivity analyses we may investigate the impact of informative missingness in our model development, i.e. departures from the missing at random assumption.

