#### 3.8. EXTERNAL VALIDATION

### 3.8.1. STUDY SETTING AND DATA COLLECTION (VALIDATION DATASETS)

The developed models will be validated on three datasets. These are:

**Brigham and Women's Hospital**: The Brigham and Women's CABG Genomics Database is a prospective single centre and detailed research database comprising over 2000 surgeries from 2001-2016. This dataset contains over 1,700 prospectively collected and curated pre, intra, and post-operative variables.

**NHS Trusts:** The study will prospectively collect data from the UK NHS Trusts which will allow us to undertake external validation of PARADISE-1/PARADISE-2 with a total of approximately 6000 patients (2000 AFACS events) per annum. The NHS Trusts where data will be extracted from are:

- Liverpool Heart & Chest NHS Foundation Trust
- Barts Heart Centre (Barts Health NHS Trust)
- Oxford University Hospitals NHS Foundation Trust

Tight K study (trial dataset): (BHF-funded CS/18/3/34063, ClinicalTrials.gov Identifier: NCT04053816). Tight K is a 22-centre clinical trial that will include 1684 patients, randomised within this non-inferiority trial to investigate whether maintaining serum potassium ≥3.6mEq/L is equivalent to maintaining levels at 4.5- 5.5mEq/L, with a primary endpoint of development of AFACS using precise clinical definitions and 5-day Holter monitoring. The trial is already designed to collect detailed data on AFACS risk factors, minimising any additional burden of PARADISE. It is restricted to patients undergoing isolated coronary artery bypass grafting. This has the strength that detailed data are being collected in a well-defined cohort, but means we need additional prospective data to assess the performance of the PARADISE scores in valve surgery.

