Both regression models and machine learning approaches will then be externally validated on prospective data from one US hospital (Brigham and Women's Hospital), prospectively collected data from UK NHS Trusts and one UK clinical trial (Tight K study). In brief, for each individual in these datasets, outcome predictions will be calculated using the model developed with the Massachusetts General Hospital dataset and compared with the observed outcomes. The performance of the prediction models will be characterised by evaluating calibration and discrimination. To account for potential differences in case-mix (distribution of patient characteristics and prevalence of the outcome) between the US data (Massachusetts General Hospital dataset) used to develop the model and the prospective external validation, we will investigate whether recalibration is needed to update the model to better fit the UK population [35].

Heterogeneity in model performance will be explored over different hospitals using internal-external cross-validation [40, 41].

Finally, we will compare our prediction models to those existing prediction models identified from the systematic review where sufficient details are available from the original publication and predictors are available in the US data set.

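### The planned comparison cannot show whether MAR holds, and the only MNAR sensitivity analysis is optional and confined to model development

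*SAP*

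**What the plan says.** SAP 3.4.1 applies MAR imputation at both stages: "To avoid excluding patients when developing and validating our models, we will use multiple imputation". It concedes that the true mechanism can seldom be identified from the data and that MNAR is not implausible. It then says it will examine MAR by "comparing the imputed values (after accounting for the observed values) and the missing values to identify if there are any systematic differences". Protocol 11.8 has the same sentence, opening "We will nevertheless explore whether the MAR assumption holds by comparing the imputed values".

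One further sentence, in the SAP only, concerns departures from MAR: "Using sensitivity analyses we may investigate the impact of informative missingness in our model development". It names no method, variables or range. The sentence before it expects the Liverpool and Barts data to give a large "prospective validation but is likely to contain more missingness"; Protocol 11.8 says the same of the NHS Trusts generally. Protocol 11.8, SAP 3.6 and SAP 3.8 contain no MNAR analysis.

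The objectives table in the Protocol makes the c-statistic and the calibration intercept and slope in external data the primary outcome.

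**The concern.** A comparison needs two sets of values, and one of these is unseen. The natural repair is to read the sentence as imputed versus observed. That is a sensible look at the imputation model, but it carries no information on whether the unseen values follow the same conditional distribution as the seen ones. It can mislead in both directions: a difference may be taken as a sign of MNAR when MAR holds, and agreement may be reported as support for MAR when it fails.

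The analysis that could address MNAR may never be run. If it is run, its stated scope is the development data, not the data that supply the primary outcome and where more missingness is expected.

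**Working it through.** **Inputs.** From the documents: 20% events (SAP 3.3.2 and 3.8.2); NHS volume of "approximately 6000 patients (2000 AFACS events) per annum", i.e. 2000/6000 = 33%; a target 95% CI width of 0.2 for O/E (SAP 3.8.2). No missing fraction is given, so missing shares and mechanisms below are assumptions.

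**Yardsticks.** The SAP's O/E sample size reproduces: SE = 0.2/(2 × 1.96) = 0.051, and n = (1 − 0.2)/(0.2 × 0.051²) = 1538. So ±0.1 is the plan's own precision target. At n = 6000 the half-width is 1.96 × √((1 − p)/(np)), which is 0.051 at 20% events and 0.036 at 33%.

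**Step 1: hold the observed data fixed and move only the unseen values.** n = 200,000; x = 0.5z + 0.87e (SD about 1); logit P(event) = −1.6 + 0.5z + 0.5x; logit P(x missing) = −1 + 0.8z. This gives 29.4% missing and 19.7% events. x is imputed under MAR from z and the outcome, and the unseen x are shifted by delta. Triplets are calibration intercept / slope / O/E of the fixed model.

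| Delta | Observed mean | Imputed mean | Unseen true mean | On imputed data | On full data |
|---|---|---|---|---|---|
| 0 (MAR) | −0.105 | 0.255 | 0.256 | −0.012 / 0.996 / 0.991 | −0.012 / 0.999 / 0.992 |
| −0.5 | −0.105 | 0.255 | −0.244 | −0.012 / 0.996 / 0.991 | 0.073 / 1.021 / 1.054 |
| +0.5 | −0.105 | 0.255 | 0.756 | −0.012 / 0.996 / 0.991 | −0.102 / 0.941 / 0.931 |
| +1 | −0.105 | 0.255 | 1.256 | −0.012 / 0.996 / 0.991 | −0.199 / 0.860 / 0.872 |

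Everything the analyst can see is the same in all four rows, so no comparison of available values can tell them apart. Imputed and observed means differ by 0.255 − (−0.105) = 0.36 even in the MAR row.

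**Step 2: how the marginal comparison behaves.** x = 0.6z + 0.8e; logit p = a + bx·x + bz·z with (bx, bz) from (0.10, 0.75) to (0.55, 0.40), model C about 0.71; 10–30% missing; missingness log-odds 0.5–1.0 per SD; x imputed from z, the outcome and their product. Imputed-minus-observed mean, at 33% events and bx of 0.20 and 0.55:

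- MAR (missingness on z): 0.28–0.55 SD, with O/E about 1.00.
- MNAR on x: 0.17–0.34 SD.
- MNAR on the residual e: 0.00–0.03 SD, although the truly missing values lay 0.37–0.72 SD from the imputed ones.

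The visible difference is largest where there is no bias.

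**Step 3: size.** Same set-up, MNAR on x, true O/E 1.00. Largest values (30% missing, log-odds 1.0):

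| Effect bx per SD | 0.10 | 0.20 | 0.35 | 0.55 |
|---|---|---|---|---|
| O/E, 33% events | 1.011 | 1.022 | 1.038 | 1.060 |
| O/E, 20% events | 1.014 | 1.029 | 1.051 | 1.081 |

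Missingness towards low values mirrors these below 1. The 0.55 case is an upper end: that predictor alone has C 0.70. Protocol 5.1 puts the best published model at 0.68, "just marginally better than a model which only included age" (0.66).

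Three incomplete predictors at 0.20 each, all missing in the same direction, reached 1.086 (33% events) and 1.112 (20%). With one running the other way the values were 1.031 and 1.043.

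**Step 4: slope and C.** In the single-predictor runs of Step 3 the slope moved by 0.03 or less and C by 0.004 or less. Step 1 shows the slope bound is not general: 0.996 on imputed data against 0.860–1.021 on full data.

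**Step 5: does a delta analysis help?** In the Step 3 set-up (33% events, 30% missing, log-odds 1.0), imputations shifted by −0.5, −0.25, 0, +0.25 and +0.5 SD gave O/E 1.042, 1.032, 1.022, 1.012 and 1.002 for bx 0.20, and 1.118, 1.089, 1.060, 1.032 and 1.005 for bx 0.55. The range shows how far the result depends on MAR, which the planned comparison cannot.

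**The case against.** **No planned estimate depends on the check.** The SAP only promises to explore, admits the mechanism is rarely identifiable, attaches no decision rule and imputes whatever is found. The sentence may be a slip for imputed versus observed. All of this stands; the harm lies in how the result would be interpreted and reported.

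**The effect looks small.** Every single-predictor shift in Step 3 is inside ±0.1. A change from 20% to 33% events is itself logit(1/3) − logit(0.2) = 0.69 if predictors do not explain it, against intercept shifts of 0.01–0.11 for bx 0.20–0.55 in those runs. This stands as a reason not to grade the point higher. But the larger shifts exceed the 0.036–0.051 sampling half-width, three predictors at 20% events pass 0.1, and the full-SD shift in Step 1 gives 0.991 against 0.872, a gap of 0.12.

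**Missingness is already being tackled.** Protocol 12.2 has research nurses extract unstructured NHS variables by hand, and the Tight K and Brigham data are described as detailed or curated. This may reduce missingness. It does not test MAR, but it is why the remedy centres on the NHS set.

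**Stronger readings to avoid.** A reader might infer that MNAR would corrupt the stated criteria for UK recalibration. SAP 3.8 says only "we will investigate whether recalibration is needed to update the model to better fit the UK population" and names neither the intercept nor O/E as the criterion; O/E is not in the primary outcome and appears only in the sample-size section. Nor do the documents leave validation data without missing-data handling: multiple imputation covers them, and the gap concerns the MNAR sensitivity analysis alone.

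**Conclusion.** The point holds and should be corrected. That the comparison cannot assess MAR is a matter of logic and rests on no simulation. That the MNAR analysis is optional and limited to development is plain from the text.

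The size of any bias is unknown. The figures of at most 0.08 on O/E for one predictor and up to 0.11 for three assume 10–30% missing, log-odds 0.5–1.0 per SD and missingness driven by the predictor itself. They illustrate and do not characterise this study; effects on the slope in particular vary with the mechanism. Nothing here shows that the external validation will be biased, only that the plan has no committed way to show how far its results depend on MAR.

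**What to change.** 1. In SAP 3.4.1 and Protocol 11.8, describe the comparison as imputed versus observed, a plausibility check of the imputation model, and drop the claim that it bears on whether MAR holds.
2. In SAP 3.4.1, replace the optional sentence with a committed, prespecified delta-adjusted sensitivity analysis in the NHS validation set, extended to Brigham or Tight K only if missingness there is material. Take the few predictors with most missing data and shift their imputations singly and together over a justified range (for example ±0.25 and ±0.5 SD, or the log-odds scale for binary predictors). Report the change in calibration intercept, slope, O/E and c-statistic of the fixed regression models.

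**Cost:** wording in two documents and modest extra analysis. The two fixed models are re-scored on shifted imputations with no refitting. The delta range is a judgement that must be defended in advance. The machine learning models, also externally validated, are left out to keep the work small.

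**Separate minor note:** SAP 3.3.5 checks normality of residuals, although SAP 3.3.4 specifies logistic regression. Raw, Pearson and deviance residuals of a correct logistic model are not normal (simulated skewness at 20% events: 1.44 deviance, 1.90 Pearson), so the check is uninformative. Delete it or specify randomised quantile residuals.

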#### 3.4.2. METHOD FOR HANDLING OUTLIERS

Outliers will be identified by plotting box plots of each continuous variable. Clinical judgment will be used to assess if the outlier could be a true value.

#### 3.5. INTERNAL VALIDATION

After developing a prognostic model, it is important to evaluate its performance. Internal validation can be performed using methods applied to the same data from which the model was developed. Internal validation of the final model will also be assessed by the bootstrap resampling technique using at least 200 iterations whereby each modelling step is repeated in each bootstrap sample, to adjust for over-optimism in the estimation of model performance. ML models will also be additionally validated via k-fold cross-validation. The internal validation will quantify and be used to adjust the performance measures (e.g., discrimination, calibration) for any optimism.

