11.2.2 Model performance and validation

The performance of a prediction model is typically assessed by its calibration and discrimination.

Calibration, which reflects how close the predictions from the model are to the observed outcome frequencies will be assessed graphically, using a calibration plot, plotting observed outcomes against predictions using smoothing techniques. The plot will also be supplemented with results for individuals grouped by similar probabilities (tenths) comparing the mean predicted probability to the mean observed outcome. Calibration will also be quantified by calculating the calibration slope and intercept.

The discrimination of the prediction models will be summarised with the concordance index (equivalent to the Area Under Receiver Operating Characteristic curve) with 95% confidence interval.

An important goal of a prediction model is to classify patients into risk groups. Both models will produce a risk score (probability) for each patient, based on their own predictor values. We will then identify a cut-off value to decide when the risk is high (such that we predict poor outcome) and when it is low (such that we predict a good outcome). The cut-off value (or range of), will be examined using decision curve analysis, which calculates the net benefit of using the model (compared to not using the model). The net benefit of a model is the difference between the proportion of true positives and the proportion of false positives weighted by the odds of the selected threshold for high-risk designation (61). The internal validity of the final models will also be assessed by the bootstrap re-sampling technique to adjust for over-optimism in the estimation of model performance. ML models will also be additionally validated via k-fold cross-validation. The internal validation will quantify and be used to adjust the performance measures (e.g. discrimination, calibration) for any optimism.

To account for potential differences in case-mix (distribution of patient characteristics and prevalence of the outcome) between the US data used to develop the model and the prospective external validation, we will investigate whether recalibration is needed to update the model to better fit the UK population (60).

Finally, we will compare our prediction models to those identified in the systematic review.

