#### 3.3.6. MACHINE LEARNING APPROACHES

In parallel to develop statistical prediction models, we will investigate machine learning (ML) approaches to developing a prediction model, including methods such as random forests, deep neural networks, and Bayesian Gaussian processes. Such models allow consideration of interactions between available variables providing "latent variables" (complex, non-linear transformations of the original input variables) that may improve prediction performance over the non-transformed input variables. We will prioritise principled, probabilistic methods that permit the incorporation of prior clinical knowledge, such that results are "interpretable", avoiding the "black box" nature of much ML-oriented research in this area [32, 33].

We will exploit the ability of the complementary modern ML fields of (i) Bayesian non-parametric modelling (which provides a principled means of coping with artefact and measurement noise in the clinical data) and (ii) deep learning, which permits the fusion of large quantities of (potentially time-varying) clinical variables. These models include components ("attention mechanisms") that allow the resulting risk estimations to be interpretable for clinicians.

Importantly, these models permit the model to quantify its uncertainty in its score prediction – where conventional medical statistical methods always output a score, ML models provide the opportunity to quantity probabilistically the certainty with which a score is produced; this offers advantages in applications in which classes are substantially overlapped, as often occurs in complex, real-world clinical problems, where there is imperfect class separation. Accuracy of such models can often be substantially improved by permitting a model not to make a classification if the score is highly uncertain; such approaches are used in many application areas of critical systems to improve acceptability with users.

Additionally, we will investigate the joint construction of phenotypical clustering models (which identify reproducible phenotypes in the physiological data) with predictive models specific to each phenotypical group – this novel approach constructs an ensemble of predictive models that are phenotype-specific, thereby improving predictive accuracy with respect to a single "one-size-fits-all" generic algorithm applied to the entire population.

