#### 3.7. CLINICAL UTILITY/NET BENEFIT

Decision curve analysis will be used to assess and compare the utility of the models (both regression model and machine learning approaches) and to explore at 25% of threshold which calculates the net benefit of using the model (compared to not using the model). The net benefit of a model is the difference between the proportion of true positives and the proportion of false positives weighted by the odds of the selected threshold for high-risk designation [36].

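### SAP 3.5 gives ML models two internal validation estimates and does not say which one counts; the bootstrap one can be badly optimistic for flexible learners

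*SAP*

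**What the plan says.** SAP 3.5 states: "Internal validation of the final model will also be assessed by the bootstrap resampling technique using at least 200 iterations". The model building is redone every time, as the SAP puts it "whereby each modelling step is repeated in each bootstrap sample". The purpose is given as "to adjust for over-optimism in the estimation of model performance. ML models will also be additionally validated via k-fold cross-validation". Protocol 11.2.2 has nearly the same text, including "ML models will also be additionally validated via k-fold cross-validation". The wording adds k-fold cross-validation to the bootstrap for ML models; it does not replace it.

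SAP 3.5 continues: "The internal validation will quantify and be used to adjust the performance measures (e.g., discrimination, calibration) for any optimism". It does not say whether the bootstrap or the k-fold result does this for ML models. It gives neither the bootstrap variant nor the number of folds.

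The ML methods in SAP 3.3.6 are described as "including methods such as random forests, deep neural networks, and Bayesian Gaussian processes", with no tuning or regularisation fixed. SAP 3.7 uses decision curves to "compare the utility of the models (both regression model and machine learning approaches", without stating whether the predictions are apparent, cross-validated or external. SAP 3.8.2 states: "Both regression models and machine learning approaches will then be externally validated on prospective data from one US hospital", and goes on to the NHS Trusts and Tight K. The protocol's primary outcome is discrimination and calibration in external data.

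**The concern.** Refitting all steps in each resample and then adjusting for optimism most naturally describes optimism subtraction. Each bootstrap model is scored in its own bootstrap sample and in the original data, and the mean difference is subtracted from apparent performance. This works for regression with few parameters relative to events. It can fail for a learner that reproduces its training data almost perfectly, because most of the original patients were also in the fitting sample. The model scores too well on both sides of the subtraction, and the estimated optimism is too small.

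Three planned uses of internal performance are exposed:

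- SAP section 4 makes internal validation a reported result.
- SAP 3.6 compares the performance of regression and ML models with and without prior AF, and section 3.8 does not expressly send the prior-AF models to external data.
- SAP 3.7 compares the two families on predictions of unstated origin.

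With two ML estimates and no rule between them, the choice could also be made after both are seen.

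**Working it through.** **The plan's own figures.** SAP 3.5 gives no performance figure to reproduce. The SAP figures used to anchor the simulation were checked first.

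- SAP 3.3.2: 12,000 surgeries, 20% events. Maximum Cox-Snell R² = 1 − exp{2[0.2 ln 0.2 + 0.8 ln 0.8]} = 0.632. Of this, 5% is 0.0316 and 15% is 0.0949 (SAP: 0.0316 and 0.0948).
- Number of parameters = n(S − 1) ln(1 − R²/S), with shrinkage S = 0.9 (assumed). This gives 42.9 and 133.6 (SAP: 42 and 132).
- SAP 3.8.2: C of about 0.72. With a normal linear predictor this corresponds to R² of 0.097 (SAP: about 0.09).

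**Overlap.** The chance that a given patient is in a bootstrap sample is 1 − (1 − 1/n)ⁿ ≈ 1 − e⁻¹ = 0.632.

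**Simulation A.** 40 normal predictors (15 with an effect), about 20% events, best achievable C 0.713, n = 12,000, 8 bootstrap resamples, 5-fold cross-validation. True C is from 40,000 new patients. Corrected C = apparent C − mean(C in bootstrap sample − C of the same model in original data). Share removed = estimated optimism / (apparent − true).

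| Model | Apparent | Estimated optimism | Corrected | k-fold | True | Share removed |
|---|---|---|---|---|---|---|
| L1 logistic | 0.709 | 0.007 | 0.703 | 0.702 | 0.710 | not defined |
| Forest, fully grown | 1.000 | 0.054 | 0.946 | 0.651 | 0.651 | 15% |
| Forest, leaf size 50 | 0.878 | 0.108 | 0.770 | 0.683 | 0.691 | 58% |
| Network, weakly regularised | 0.938 | 0.148 | 0.791 | 0.617 | 0.605 | 44% |
| Network, strongly regularised, briefly trained | 0.744 | 0.073 | 0.671 | 0.692 | 0.702 | over 100% |

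For the fully grown forest, 0.054 / (1.000 − 0.651) = 15%. Its corrected C is 0.946 − 0.651 = 0.295 too high, and it ranks above a regression that is better in new patients (0.710).

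**Simulation B.** A separate run of the same size (event rate 0.197, 40 predictors, best C 0.71, 5-fold cross-validation):

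| Model | Corrected | k-fold | True |
|---|---|---|---|
| Logistic | 0.716 | 0.716 | 0.708 |
| Forest, fully grown | 0.946 | 0.664 | 0.656 |
| Forest, leaf size 20 | 0.818 | 0.697 | 0.686 |
| Forest, leaf size 100 | 0.724 | 0.699 | 0.689 |
| Two-layer network | 0.770 | 0.642 | 0.633 |

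The corrected figures rank the forests in the reverse of their true order. A second seed (event rate 0.175) gave 0.939 against 0.649 for the fully grown forest.

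**Smaller sample.** With n = 3,000, 10 resamples and 10-fold cross-validation, corrected / k-fold / true C was 0.942 / 0.624 / 0.644 for the fully grown forest and 0.850 / 0.612 / 0.616 for the weakly regularised network. An early-stopped network was unstable there (apparent 0.580, k-fold 0.593, true 0.558) and is not relied on.

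**Other bootstrap variants, Simulation A.** Out-of-bag C was 0.642 for the fully grown forest and 0.600 for the weakly regularised network, close to the true 0.651 and 0.605. The plain .632 estimate was still high (0.773 and 0.724). The .632+ estimate was not run but follows approximately from these figures, taking 0.5 as the no-information C:

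- Fully grown forest: R = (1.000 − 0.642)/(1.000 − 0.5) = 0.716. Weight = 0.632/(1 − 0.368 × 0.716) = 0.858. Estimate = 0.142 × 1.000 + 0.858 × 0.642 = 0.693.
- Weakly regularised network: R = (0.938 − 0.600)/(0.938 − 0.5) = 0.772. Weight = 0.883. Estimate = 0.117 × 0.938 + 0.883 × 0.600 = 0.640.

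These are about 0.04 too high (0.693 − 0.651 = 0.042; 0.640 − 0.605 = 0.035): far better than optimism subtraction, less accurate than k-fold.

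**The case against.** The strongest reply is that the plan already contains a sound estimate. K-fold cross-validation is planned for every ML model, and a bootstrap C of 0.946 beside a k-fold C of 0.651 would alert any statistician. Both model families also go to three external datasets, where the primary outcome is measured, and nothing says the choice between regression and ML rests on internal figures. The bootstrap variant is not named, so an out-of-bag estimator would fit the wording. The tuning values simulated are not from the documents, and Gaussian processes were not simulated.

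Most of this stands and limits the point. A reader might infer that internal ML performance will be far too high, that the bootstrap barely corrects any ML model, or that ML will be declared better on the only evidence available before external data. The documents do not support that. The share of optimism removed ran from 15% to over-correction according to tuning, and the k-fold results also exist before external data; in both simulations they do not favour ML.

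The reply does not remove the gap. Nothing in SAP 3.5 gives the k-fold figure precedence, and the bootstrap is the method described there as adjusting for over-optimism. An analyst who followed the text could report the biased figure and be within the plan.

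**Conclusion.** The concern holds in a limited form: SAP 3.5 prescribes two internal estimates for ML models that can differ by about 0.29 in C (0.946 against 0.651), and leaves open which one is used. Under optimism subtraction, internal ML performance could be overstated by roughly 0.14 to 0.19 for a weakly regularised network (0.770 − 0.633; 0.791 − 0.605) and 0.29 to 0.30 for a fully grown forest, enough to rank either above a better regression. For a strongly regularised network the error was −0.03 (0.671 − 0.702).

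This rests on the optimism-subtraction reading, on illustrative tuning, on simulated truths of one type, and on few resamples in Simulation A (8, against the SAP's minimum of 200), although a bias of this size is not resampling noise. The external performance estimates, and so the primary outcome, are not affected. The point should be settled before ML results are seen, but it does not threaten the study's main conclusion.

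**What to change.** In SAP 3.5:

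- Keep the optimism bootstrap for the regression models and name the variant.
- For ML models, state that internal C, calibration slope and calibration intercept are reported and adjusted from k-fold cross-validation, preferably repeated, and not from optimism subtraction. Give the number of folds. Put all tuning and imputation inside the folds; SAP 3.4.1 includes the outcome in the imputation model, so imputing before splitting would let held-out outcomes shape the imputed predictors. An out-of-bag bootstrap would also serve. A .632+ bootstrap is acceptable but may stay somewhat optimistic for near-memorising models; plain .632 should not be used.
- Run the same folds for regression whenever the two families are compared internally, including in SAP 3.6.

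In SAP 3.7, state that the decision curves use cross-validated or external predictions. Protocol 11.2.2 can refer to the SAP for the detail.

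The cost is wording and a small amount of extra cross-validation for regression. Computing falls overall if at least 200 bootstrap refits of each ML model are no longer needed. The internal ML figures will probably look less favourable.
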